### ***18.3. Patient Termination***

A study patient will be terminated if the study patient develops any severe adverse event that may be related to the study. A study patient will receive appropriate treatment at the discretion of the investigator. Notification of termination will be clearly documented. These study patients are considered to have completed the study and will not be replaced.

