### 3. GENERAL INFORMATION

Objective	To quantify and provide a normative standard for refractive and visual outcomes in eyes with significant corneal astigmatism undergoing cataract surgery with the Alcon Toric ReSTOR lens. As well as to quantify the postoperative rotational stability of the IOL.
	The hypothesis is that the addition of toricity will not affect the general performance of the ReSTOR design. As such, it is expected that patients with a ReSTOR toric IOL that achieve a correction of their astigmatism will have visual acuity and visual quality similar to patients implanted with the non-toric ReSTOR models. The Toric ReSTOR lenses (+2.5 and +3.0) will result in a residual refractive cylinder similar to that observed in patients with non-clinically significant astigmatism treated with non-toric ReSTOR lenses. They will also provide excellent distance and near vision in the vast majority of patients; we expect 75% of patients will have 20/25 (0.1 logMAR) or better uncorrected visual acuity at distance and near. The Toric-ReSTOR lens will demonstrate rotational stability that meets or exceeds the recommendations established by the American National Standards Institute.
Test Article(s)	Alcon Toric-ReSTOR +2.5 and +3.0 models
Control Article(s)	None.
Sample size	64 eyes of 32 subjects at 1 clinical site
Study Population	Subjects $\geq$ 30 years of age presenting for cataract surgery or refractive lens exchange surgery who are interested in astigmatism reduction and presbyopia correction. Subjects must be eligible for bilateral multifocal toric lens implantation.
Number of sites	One
Study Design	Prospective, non-randomized, single-arm, single center, open-label study.
Masking	None

Variables

Primary:

- Residual refractive cylinder

Secondary:

- Monocular and binocular Uncorrected and Best-corrected distance, intermediate (60cm) and near (40cm) visual acuity
- Postoperative orientation changes with the Toric ReSTOR IOL up to 3 months after surgery.
- Binocular Uncorrected and Best-corrected defocus curve (3 month visit).
- Quality of vision, measured with a subjective questionnaire.

Duration / Follow-up    Preoperative to 3 months postoperative

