## 5. INTRODUCTION

In the past, patients with significant corneal astigmatism undergoing cataract surgery were given only the option of a monofocal astigmatism-correcting intraocular lens (IOL). Recently, the US FDA has approved intraocular lenses for the correction of astigmatism and presbyopia; these include toric-accommodating, toric-extended depth of focus, and now toric-multifocal (Toric-ReSTOR) IOLs. Patients implanted with non-toric ReSTOR lenses (2.5 and/or 3.0) have exhibited very good vision and high rates of satisfaction with their vision at various distances. Until recently, patients with corneal astigmatism could not take advantage of this option without considering a secondary procedure such as a corneal relaxing incision or refractive surgery. (More than 0.50D of expected postoperative refractive astigmatism has been suggested to materially affect visual quality and satisfaction after multifocal IOL implantation.) The availability of toric versions of the ReSTOR 2.5 and 3.0 lenses now allows for multifocal implantation in eyes with corneal astigmatism.

Postoperative rotational stability is an important consideration with any toric IOL. In general, each degree of misalignment or misorientation of an IOL will decrease the intended astigmatic correction by 3.3%, reducing the resultant image quality. The American National Standards Institute has established an IOL rotation stability standard requiring at least 90% of lenses to exhibit less than 5 degrees of rotation. Recent single-piece IOL studies have shown the AMO toric monofocal platform exhibits less than 5 degrees of rotation in 94.1% of eyes at the 6 month period. Multiple studies reviewing the Alcon toric-monofocal platform reveal similar rotational stability, with 95-96% of lenses showing less than 5 degrees of rotation.

The expectation is that the addition of toricity will not affect the general performance of the ReSTOR design. As such, it is expected that patients with a ReSTOR toric IOL that achieve a correction of their astigmatism will have visual acuity and visual quality similar to patients implanted with the non-toric ReSTOR models.

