#### 9.3.5. Postoperative 1 Month

All routine postoperative measures will be taken. In addition, the subject will undergo manifest refraction, IOP measurement, VA testing and dilated Verion photographs to document the postoperative orientation of the IOL. Adverse events will be monitored.

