#### 9.3.6. Postoperative 3 Months

All routine postoperative measures will be taken. In addition, the subject will undergo manifest refraction, IOP measurement, VA testing and dilated Verion photographs to document the postoperative orientation of the IOL. The patient's quality of vision will be measured using a validated, Rasch-scored questionnaire. A defocus curve in accordance with the specifications below (Section 9.4) will also be obtained at this visit. Adverse events will be monitored. An exit form will be completed.

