#### 9.3.8. Exit Procedures

In the event of premature exit from the study, all study related examinations should be completed where possible. The Exit CRF should be completed, noting that the subject did not complete the study and the reason for premature study exit. If no premature exit from the study occurs, the Exit CRF should be completed at the end of Visit 6 (Postoperative 3 Months).

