### ***9.6. Discontinued Subjects***

Discontinued subjects are those who do not have an exit visit or who come into the office to be exited prior to the scheduled final study visit. Subjects may be discontinued from the study at any time if, in the opinion of the investigator, their continued participation in the study poses a risk to their health. The reasons for discontinuation include:

- a. Adverse event;
- b. Lost to follow-up;
- c. Subject decision unrelated to an adverse event;
- d. Protocol violation;
- e. Treatment failure;
- f. Other.

To ensure the safety of all subjects who discontinue prior to Visit 6, investigators should assess each subject and, if necessary, advise them of any therapies and/or medical procedures that might be needed to maintain their health. Any changes in medical health and/or use of concomitant medications should also be captured.

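### Section 18.3 ends participation for every severe, possibly related adverse event and counts those patients as completers, so refraction and rotation data can be lost for an outcome-related reason and the loss hidden

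*Combined protocol and SAP*

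**What the plan says.** Section 18.3 sets a mandatory rule: "A study patient will be terminated if the study patient develops any severe adverse event that may be related to the study". It has no test of risk and does not provide for continued study assessments. It goes on: "These study patients are considered to have completed the study and will not be replaced".

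Three other sections deal with the same situation differently.

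- **9.6** makes discontinuation optional, where "in the opinion of the investigator, their continued participation in the study poses a risk to their health". It lists adverse event among the reasons, and it defines as discontinued anyone exited before the scheduled final visit.
- **18.1** treats a patient as having completed the study once Visit 6 is done.
- **9.3.8** covers early leavers: "In the event of premature exit from the study, all study related examinations should be completed where possible". The Exit CRF must then record that the subject did not complete the study.

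On data collection, 9.3.5 says that at 1 month "the subject will undergo manifest refraction, IOP measurement, VA testing and dilated Verion photographs to document the postoperative orientation of the IOL". Section 9.3.6 repeats the refraction and the "dilated Verion photographs to document the postoperative orientation of the IOL" at 3 months. Table 15.1 schedules no other postoperative refraction or orientation photograph. The general information section expects that the lens "will demonstrate rotational stability that meets or exceeds the recommendations established by the American National Standards Institute", and the introduction describes that standard as "requiring at least 90% of lenses to exhibit less than 5 degrees of rotation".

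The intensity definitions in the adverse event section reserve *severe* for incapacitating events.

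**The concern.** In a drug trial, stopping after a severe related event can end exposure. Here the lens is already implanted, so ending participation mainly stops the scheduled measurements. The patients removed are those with a bad postoperative event that may be due to the study, so the reason for missing data is tied to outcome. There is no concurrent arm to share the loss, and section 10 gives no rule for missing data.

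The study is meant to set a normative standard, show residual cylinder non-inferior to a literature value and meet a rotation standard. Each rests on the eyes that are measured. Calling terminated patients completers adds a reporting problem: a completion count based on 18.3 could show no loss while primary data are missing.

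**Working it through.** **1. What data exist, by time of termination** (visit windows from Table 9.3-1; assessments from Table 15.1)

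| Terminated | Scheduled refraction and postoperative orientation photograph already taken | Added by a 9.3.8 exit examination, if done | 3-month value |
|---|---|---|---|
| Before Visit 5 (window opens 30 − 7 = day 23) | None; only the end-of-surgery photograph | One set, at exit | None |
| Between Visit 5 and Visit 6 (window opens 90 − 15 = day 75) | Visit 5 set | One more set, at exit | None |

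It is unclear whether 9.3.8 reaches patients whom 18.3 calls completers.

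**2. Status of a patient terminated at week 2.** Under 18.3, completed. Under 18.1, not completed. Under 9.6, discontinued. Under 9.3.8, the Exit CRF says not completed. These cannot all be followed.

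**3. The plan's own figure.** Section 11 gives SD 0.32 D, margin 0.25 D, power 0.9 and alpha 0.05. With two equal groups, no true difference and one-sided alpha:

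n = 2 × [(1.645 + 1.282) × 0.32 / 0.25]² = 28.1, rounded up to 29 per group.

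This reproduces the stated 29, and 29 × 1.10 = 31.9 gives the 32 enrolled. With an assumed 29 in the literature group, power is 0.914 with 32 patients, 0.902 with 29 and 0.897 with 28. Losing a few patients costs little power, so the issue is selection.

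**4. Illustration for cylinder.** Assume that one patient's residual cylinder averages x over both eyes and the other 31 patients average 0.40 D (the section 11 reference). Leaving that patient out lowers the mean by (x − 0.40)/32. The range for x is the eligible corneal range in 7.2, as if the toric correction were lost. At the 3.3% per degree in the introduction, that takes about 30 degrees of rotation (30 × 3.3% = 99%).

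- x = 1.0 D: 0.60/32 = 0.019 D, or 7.5% of the margin
- x = 1.5 D: 1.10/32 = 0.034 D, or 13.8%
- x = 2.5 D: 2.10/32 = 0.066 D, or 26.3%

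If only one eye is affected, these halve.

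**5. Illustration for rotation.** With 60 of 64 eyes stable (93.8%), losing one patient gives 59/62 = 95.2% if one of that patient's eyes had rotated, or 60/62 = 96.8% if both had. That is a gain of 1.4 to 3.0 points.

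The 90% threshold needs 58 of 64 eyes (0.90 × 64 = 57.6) or 56 of 62 (0.90 × 62 = 55.8). Losing a patient with one rotated and one stable eye reverses the result only at exactly 57 stable: 57/64 = 89.1% fails and 56/62 = 90.3% passes. The introduction cites stability of 94.1% to 96%, so p for rotation is 0.059 to 0.04. With independent eyes, the binomial probability of exactly 7 of 64 rotating is 0.048 at p = 0.059, 0.026 at p = 0.05 and 0.010 at p = 0.04. The chance that one of those patients is also terminated would reduce this further.

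**6. How often the rule would act.** The documents give no event rate. At assumed per-patient rates of 1%, 2% and 5%, the chance of at least one termination among 32 is 1 − (1 − r)³² = 28%, 48% and 81%, with 0.3, 0.6 and 1.6 patients expected.

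**The case against.** The best case for leaving 18.3 alone has five parts.

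- **The trigger is not the endpoint.** Severe means incapacitating, and nothing in the documents links that to cylinder or rotation. A reader might infer that the rule removes the worst refractive results; the text does not support that. A severe event could leave alignment normal, and a badly rotated lens might be graded moderate. This stands, and it limits the claim to a likely direction of bias.
- **9.6 is not as opposed as it looks.** A reader might infer that 9.6 permits discontinuation only for health risk. It does not say so, and it lists adverse event, treatment failure and other reasons. The conflict is mandatory against discretionary. This stands.
- **The 3-month value is not named as the primary.** The primary variable has no stated time point, and rotation is assessed up to 3 months, so Visit 5 or exit data could be used. This stands in part. Complete loss needs termination before Visit 5 and no exit examination, but 9.3.8 asks for that examination only where possible and cannot supply a 3-month measurement.
- **The missing value may not be the bad one.** Section 18.3 provides for treatment, and a corrected lens might give a good 3-month result. This stands as a limit on the size.
- **Safety reporting is intact.** Section 10.1 keeps all enrolled subjects in the safety evaluation, 13.4 maintains medical follow-up, and the Exit CRF records the reason. This stands, but it does not replace study refraction and photographs.

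None of this resolves the conflict over who is a completer, or gives a reason to stop measuring an implanted eye when there is no judged risk.

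**Conclusion.** The point holds as a cheap improvement. Section 18.3 contradicts 18.1 and the last-visit definition in 9.6 on completion, and replaces the judgement in 9.6 with an automatic rule. Followed as written, it ends scheduled refraction and orientation measurement for an outcome-related reason, and its completer label would conceal that. Any bias in this single-arm study is more likely to flatter the results than to worsen them.

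The size is unknown and probably small. No event rate is given, severe events should be few, and nothing changes if none occurs. The figures of 0.019 to 0.066 D and 1.4 to 3.0 points are per-patient illustrations. They assume large rotation or actual lens instability, a severe grade, no usable earlier or exit data and no correction before Visit 6; the cylinder range also assumes both eyes are affected. A reader might infer that the rule could overturn the non-inferiority or rotation conclusion. One patient moves the mean by about a quarter of the margin at most under these assumptions, and the one-rotated-eye reversal needs a boundary result with a 1% to 5% chance before the chance of termination is applied. The documents do not support a stronger claim.

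**What to change.** Replace the first and last sentences of 18.3 with text to this effect:

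> A patient with a severe adverse event possibly related to the study remains in scheduled follow-up through Visit 6, unless the patient withdraws or the investigator judges under 9.6 that staying in the study would endanger their health. A patient who leaves before Visit 6 because of such an event is classed as discontinued due to an adverse event, has the 9.3.8 exit examinations where possible, and is not replaced.

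Then:

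- Change 18.5, which closes the study at Visit 5, to Visit 6.
- Beside each 3-month result, report the number of eyes without Visit 6 data.
- Flag values taken after any secondary lens procedure.

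The intraoperative exclusions in 7.4 need not change, so this helps only with events after uncomplicated surgery. The efficacy set in 10.1 refers to arcuate incisions, which 7.3 excludes. That affects every patient and needs its own correction.

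The cost is a short protocol amendment with ethics approval. The visits, tests and $300 payment for attending the 3-month visit (9.1) are already planned for all 32 patients. Safety is kept through 9.6 and the right to withdraw in 18.2. The reported results may be slightly less favourable.

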### ***18.4. Study Termination***

The investigator with appropriate notification may terminate the study. If, after clinical observations, the investigator feels that it may be unwise to continue the study, he may stop the study.

### ***18.5. Study Completion***

The study will be complete when all enrolled patients have completed Visit 5 or have been terminated from the study.

## 19. SUMMARY OF RISKS AND BENEFITS

### *19.1. Summary of risks*

The femtosecond laser system to be used in this study is approved for corneal incisions, either full thickness or partial thickness, at the time of cataract surgery. The current study involves creating partial thickness arcuate incisions at a time after cataract surgery.

The most common side effects of arcuate incisions include:

- Irregular astigmatism
- Regression, where the effects of the incision(s) are lower over time

### *19.2. Summary of benefits*

For patients undergoing cataract surgery, they may be offered the option to have a femtosecond laser system create arcuate incisions on the cornea, with the goal of reducing corneal astigmatism (and, by extension, postoperative refractive astigmatism) at the time of surgery.

It is likely that corneal incisions made with a femtosecond laser system will reduce corneal astigmatism, even when applied after successful cataract surgery.

The potential benefit related to the current study is that this procedure could be offered to patients who have had cataract surgery in the past and who have residual refractive astigmatism with a minimal spherical equivalent refraction after surgery.
